12.1.2 Immunogenicity

Primary analysis is to calculate the 2-sided 95%CI for the difference in proportion seropositive at day 91. If lower limit of difference greater than -5% then conclude non-inferiority. If lower limit of difference greater than 0% then conclude superiority.

Secondary analyses will include calculation of 95% confidence intervals for seropositivity, seroconversion and geometric means as well as multivariable logistic and normal errors regression adjusting for covariates.

Secondary analysis of factors associated with seroconversion/response, including:

- pre-vaccination titre
- Age (9m,10m,11m) (also look at interaction with intervention)
- Sex (also look at interaction with intervention)
- PHC
- Crying when vaccine given? (also look at interaction with intervention).
- (Another factor we considered before was acute respiratory infection)
- Explanatory variables for stratification of safety profile

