Baseline: Age in months, sex, usual health care provider, heart rate, respiratory rate, temperature, height for age, weight for age, any abnormality discovered on systemic examination, pre existing medical conditions (Table 11.12.6.1B)

Others: Observations during vaccination (Table 11.12.6.1D)

The distribution of the baseline covariates by study arm will be described, but not formally tested as randomization will have ensured that any differences are chance differences. For the main comparison of the study arms adjustment for these covariates is not necessary. To investigate the effect of these covariates on study end-points multivariable logistic regression (for binary end points) or normal errors regression (on logged antibody levels) will be performed. Study arm will be included in these analyses and interactions examined as given in section 11.11.

11.10 Sub-group analyses:

No sub group analyses have been planned.

11.11 Interactions with study arm:

Potential interactions will be examined for the following co-variates: sex, age, crying during measles vaccination, and acute respiratory infection.

11.12 Descriptive Analyses:

11.12.1 Distributions of continuous variables and any agreed transformations:

Mean, standard deviation, median, and interquartile range will be generated for continuous variables. The PRNT values will be doubled if the value is >20,000. The PRNT values will be \log_{10} transformed for further analyses such as GMT and 95% CI. Results at the lower limit of the assay will be assigned a value of 10. OD values will also be \log_{10} transformed to calculate geometric means and perform regression. Any OD results of <0.01 will be assigned a value of 0.005 prior to \log_{10} transformation.

11.12.2 Distributions of binary and categorical variables:

Frequency distributions will be shown for binary and categorical variables. The categories will be checked against the Annotated CRF.

11.12.3 Outliers:

For \log_{10} PRNT values, checks for outliers will be performed prior to the statistical analysis as part of the data checking. The outliers will also be examined using standardized residuals >3 when looking at \log_{10} PRNT values.

SOP VEL 1/1:
September 11, 2012

Phase II/III	WHO Measles Aerosol Vaccine	Protocol
Clinical Trial	Project	WHO/MAP/IN/002

11.12.4 Flow of Numbers:

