	n		% (95% CI) for difference		
	AER	SC	AER	SC	
Seropositivity at day 0					
Seropositivity at day 28					
Seropositivity at day 91					
Seropositivity at day 364					

12.3 Risk factor Analyses:

As covariates for inclusion in multivariable analyses: age; weight for age; sex; day 0 antibody titre; study site; crying when vaccine given (aerosol arm only); presence of respiratory tract symptoms at time of vaccination (aerosol arm only).

	Seropositivity [*]					
Risk Factors/Covariates	OR	95%CI	Р			
Age (months):	•					
9	1.0					
10						
11						
11.99						
Sex (Male)						
Usual health care provider						
Government	1.0					
Private						
Non-governmental organization						
others						
Weight for Age						
Normal	1.0					
Abnormal						
Height for Age						
Normal	1.0					
Abnormal						
Day 0 Antibody Titre						
Sites:						
Vadu	1.0					
Pabal						
Talegoan Dhamdhere						
Nhavare						
Chakan						
Shel Pimpalgaon						
Wagholi						
Alandi						
Crying when vaccine given (yes):						
Respiratory Track Symptoms at the time of vaccination (Yes)						
Any abnormality discovered on systematic examination(Yes)						
Pre existing medical condition(Yes)						

 Table 12.3.1: Risk Factors for Seronegative of Aerosol Arm children

*Modelled for seronegatives.

SOP VEL 1/1:	Statistical Analysis Plan	Page 32 of 61
September 11, 2012		

Phase II/III	WHO Measles Aerosol Vaccine	Protocol
Clinical Trial	Project	WHO/MAP/IN/002

13.0 Safety Analyses:

13.1: Reactogenic Events:

Table 13.1.1A (1): Frequency of adverse events reported during the first 30 minutes after vaccination

	Aerosol				Subcutaneous			
Adverse Events	Number	% of AE	95% percenta	95% CI for ercentage of AE Nu		% of AE	95% CI for percentage of AE	
	OI AES		Lower CI	Upper CI	OI AES		Lower CI	Upper CI

 Table 13.1.1A (2): Number of subjects experiencing at least one adverse event during the first 30 minutes after vaccination

	Aerosol				Subcutaneous			
Adverse Events	Number of persons	Number of persons		95% CI for Population		Proportion in	95% CI for Population	
having AE [#]	population ** (in %)	Lower CI	Upper CI	having AE [#]	** (in %)	Lower CI	Upper CI	

[#]One subject may have more than one AE. So, 'Number of persons having AE' counts expected to overlap

Phase II/III	WHO Measles Aerosol Vaccine	Protocol
Clinical Trial	Project	WHO/MAP/IN/002

Table 13.1.1B (1): Frequency of adverse events reported from 31 minutes 14 days after

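### The only table planned for the covariate models (SAP Table 12.3.1) is limited to the aerosol arm, so it cannot show the arm-adjusted effects or arm interactions that SAP 11.9 and 11.11 and protocol 12.1.2 call for

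*Supplement*

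**What the plan says.** **Model described in the text.** SAP 11.9 plans multivariable logistic regression for binary endpoints and normal-errors regression for logged antibody levels, and adds: "Study arm will be included in these analyses and interactions examined as given in section 11.11". SAP 11.11 then lists them: "Potential interactions will be examined for the following co-variates: sex, age, crying during measles vaccination, and acute respiratory infection". Protocol 12.1.2 asks for the same kind of analysis: "Age (9m,10m,11m) (also look at interaction with intervention", "Sex (also look at interaction with intervention", and likewise for crying.

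**Which covariates are tied to one arm.** The text of SAP 12.3, like protocol 9.2, limits two covariates only: "crying when vaccine given (aerosol arm only); presence of respiratory tract symptoms at time of vaccination (aerosol arm only". Age, sex, day 0 titre and study site carry no such limit.

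**The output.** SAP 12.3 has one table, 12.3.1, titled "Risk Factors for Seronegative of Aerosol Arm children" and footnoted "Modelled for seronegatives". All its covariates, including age, sex, titre and site, fall under that title. It has no row for study arm or for any interaction. No other shell reports a covariate model: Tables 17.1.1.1 and 17.2.1.1 give arm differences by vaccination sequence number and by site.

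**The concern.** A model fitted to aerosol infants alone answers one question: which factors go with seronegativity among aerosol recipients. The SAP text poses two others: what effect a covariate has in the trial once arm is allowed for, and whether that effect differs by route. The table can answer neither.

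The second question matters here. Protocol 4.3.1.2 reports that below 10 months of age seroconversion was lower with aerosol than with injection in four comparative studies. It calls the studies in that age group heterogeneous, and in only two of the four was the difference unlikely to be chance. The trial enrols infants from 9.00 to 11.99 months. If the youngest infants respond less well, readers will want to know whether that holds for any measles vaccine or for the aerosol in particular. The age odds ratio in Table 12.3.1 mixes the two.

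Restricting the table also leaves out the subcutaneous seronegatives, in a model that already has many terms for its events.

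**Working it through.** **1. The plan's own figure.** Inputs from SAP 8.1: 90% seropositive in both arms, margin 5 points, one-sided 2.5%, power 90%, 20% loss, 2000 enrolled and 1600 evaluable. Allocation is 1:1 (protocol 6.3.1.2).
- Normal approximation: n per arm = (1.960 + 1.282)² × 2 × 0.9 × 0.1 / 0.05² = 757, or 1514 in total.
- With continuity correction: (757/4) × (1 + √(1 + 4/(757 × 0.05)))² = 796.5, so 797 per arm and 1594 in total, which agrees with 1600.
- Power at 800 per arm: Φ(0.05/√(0.18/800) − 1.960) = 91.5%.
- 1600 / 0.80 = 2000.

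The design figure reproduces, so 800 evaluable per arm is a fair base. The documents give no event count for Table 12.3.1.

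**2. Seronegatives used and left out.** Events per arm = 800 × (1 − seropositivity).

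| Aerosol / subcutaneous seropositive | Aerosol events | Subcutaneous events | Share left out |
|---|---|---|---|
| 90% / 90% (SAP assumption) | 80 | 80 | 80/160 = 50% |
| 87% / 90% (assumed) | 104 | 80 | 80/184 = 43% |
| 85% / 90% (assumed) | 120 | 80 | 80/200 = 40% |
| 93.5% / 97.1% (pooled rates for 10–36 months, protocol 4.3.1.2) | 52 | 23 | 23/75 = 31% |

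The share keeps falling as the gap widens: at an assumed 85% / 95% it is 40/160 = 25%.

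**3. Parameters in Table 12.3.1.** Age 3, sex 1, provider 3, weight for age 1, height for age 1, day 0 titre 1, site 7, crying 1, respiratory symptoms 1, systemic abnormality 1, pre-existing condition 1: 21 in all. The table gives age four rows (9, 10, 11, 11.99), but Table 11.12.6.1A and protocol 12.1.2 have three groups. With three groups the count is 20.

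**4. Events per parameter at 90% / 90%.**

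| Model | Age in four rows | Age in three groups |
|---|---|---|
| Aerosol only | 80/21 = 3.8 | 80/20 = 4.0 |
| Both arms plus arm term | 160/22 = 7.3 | 160/21 = 7.6 |
| Plus the four SAP 11.11 interactions | 160/28 = 5.7 | 160/26 = 6.2 |

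**5. Precision.** Take a binary covariate with 50% prevalence (an assumption) and a 10% event rate. SE of the log odds ratio = 1/√(N × 0.5 × 0.5 × 0.1 × 0.9). The odds ratio detectable with 80% power at two-sided 5% is exp(2.80 × SE).
- Aerosol only, N = 800: SE 0.236, detectable odds ratio 1.94.
- Both arms, N = 1600: SE 0.167, detectable odds ratio 1.60.
- Arm interaction, two arms of 800: SE = √2 × 0.236 = 0.333, detectable ratio of odds ratios 2.54. From one arm it cannot be estimated.

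**6. The text against itself.** SAP 12.3 and protocol 9.2 confine crying and respiratory symptoms to the aerosol arm. SAP 11.11 lists arm interactions for crying and acute respiratory infection, and protocol 12.1.2 does so for crying. An interaction with arm needs the covariate in both arms. Table 11.12.6.1D already tabulates crying during vaccination for both.

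**The case against.** The best reply is that nothing is missing from the plan. SAP 11.9 and 11.11 specify the two-arm model, SAP 9.2 leaves the final format of tables until after the pre-analysis review, and other planned analyses, such as the regression on logged antibody, have no shell either. Table 12.3.1 says plainly whom it covers and does not claim that its factors are specific to the aerosol. The analysis is secondary: SAP 11.9 does not require adjustment for the main comparison, 11.10 plans no subgroup analyses and 11.7 sets no fixed significance level for covariate work.

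Much of this stands and keeps the point modest. It does not remove the conflict, because the population and terms of a model are more than table format.

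A reader might infer more than the documents support:
- **That the two-arm analysis was dropped.** It remains in the text; only its output is lacking.
- **That the table tests general non-response, or gives false positives.** It mixes shared and route-specific predictors. If an age effect exists in both arms, finding it among aerosol infants is a true positive. Setting that rejection rate beside the error rate of an interaction test compares two different hypotheses.
- **That half the events are always lost.** This holds only when seropositivity is equal in the two arms.
- **That using both arms cures the sparse-data problem.** It helps, but the full interaction model still has only about 6 events per parameter.

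**Conclusion.** The point holds as an inconsistency between the SAP text and its table shell. As written, Table 12.3.1 cannot report the arm-adjusted covariate effects of SAP 11.9 or the interactions of SAP 11.11 and protocol 12.1.2, and no other shell does.

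At the SAP's planning values it draws on 80 of 160 seronegatives, giving about 4 events per parameter against 7.3 to 7.6 with both arms and an arm term. These figures rest on 800 evaluable infants per arm and 90% seropositivity in each. If aerosol is less immunogenic, the share left out is smaller (31% to 43% in the three cases tabulated). The detectable odds ratios also assume 50% covariate prevalence.

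The affected analysis is secondary. The seropositivity difference, its confidence interval and the non-inferiority conclusion do not depend on it.

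**What to change.** - Fit Table 12.3.1 to both arms, with a study-arm row and rows for the SAP 11.11 interactions. Beside each interaction give the odds ratio in each arm. Retitle the table to match.
- If an aerosol-only model is still wanted, keep it as a labelled supplement with the same covariate adjustment.
- Reconcile the aerosol-only limit on crying and respiratory symptoms (SAP 12.3, protocol 9.2) with their listed arm interactions (SAP 11.11; protocol 12.1.2 for crying). State whether respiratory symptoms and acute respiratory infection are the same variable.
- Use the three age groups of Table 11.12.6.1A.

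The cost is revised shell wording and a few more model terms. No new data should be needed: crying is already tabulated for both arms, and protocol 8.5.1.2 has a history and examination recorded for every child on day 0. The downside is a little more analysis work and interaction estimates of limited precision (a detectable ratio of odds ratios of about 2.5 in the case above), so they should be read from their confidence intervals, as SAP 11.7 already intends.

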The sample size will be 100 in each arm at each of day 28 and day 364. Based on the estimated variability (Standard deviation) of post subcutaneous vaccination PRNT results of 0.43 on a \log_{10} scale ([name], Health Protection Agency London, personal communication) differences of <1.5 fold in geometric mean titres between aerosol and subcutaneous groups at each time point and between each time point would be able to be detected at a 5% significance level with 80% power.

8.2 Safety:

To estimate proportions with AE in Aerosol and Subcutaneous groups, the sample sizes above give acceptable precision.

SOP VEL 1/1:	Statistical Analysis Plan	Page 6 of 61
September 11, 2012		

Phase II/III	WHO Measles Aerosol Vaccine	Protocol
Clinical Trial	Project	WHO/MAP/IN/002

Table 8.2.1: Range of Precision with	Different Leve	els of Proportions	Experiencing
Event and Numbers of Participants.			

Observed	95% confidence intervals	
proportions	N=800	N=1000
0%	0.00 - 0.46%	0.00-0.37%
1%	0.43-1.96%	0.48-1.83%
2%	1.15-3.23%	1.26-3.07%
5%	3.60-6.75%	3.73-6.54%

The table shows that, if no reactions are observed, the upper 95% confidence interval with a sample size of 1000 is 0.37%, or 1 in 270.

9.0 Data Management and Pre-analysis Statistical Review:

9.1 Data Management:

The data management plan has been developed by the CDMC, Dept., of Biostatistics, Christian Medical College, Vellore. For more details refer to SOP 04/02 Clinical Data Management.

9.1.1 Data Quality Control, Query management and Quality Assurance:

Please refer SOPs Query Generation and Resolution (15/02) and Quality control and Quality assurance (16/02) for details.

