9.2 Pre-analysis Statistical Review

This pre-analysis review will be used to make decisions about issues including the exclusion of subjects or data from analysis sets, possible data transformations, and identification of outliers. Important covariates identified in recent research studies might be specified at this stage. The final format of tables will be decided after this review. Decisions taken during the pre-analysis review will be documented.

The steps to be taken in the pre-analysis review are as follows:

1. Each database (e.g. laboratory data, AE data, etc.) will be imported to SAS software format.

SOP VEL 1/1:	Statistical Analysis Plan	Page 7 of 61
September 11, 2012		

Phase II/III	WHO Measles Aerosol Vaccine	Protocol
Clinical Trial	Project	WHO/MAP/IN/002

2. Basic frequencies and distribution tables and/or plots will be performed for each variable. For example, histograms will be made for continuous variables, such as age, height and weight, etc.

10.0 Description of Patient Flow and Analysis Datasets:

The flow of participants through the trial and follow up will be described in flow charts, as recommended by the CONSORT group (2). The flow diagrams will describe the numbers at each stage and will summarize reasons for exclusion for a 'per-protocol' dataset and an 'intention to treat' dataset (Figures 11.12.7.1 to 11.12.7.3). Tables describing the numbers excluded at each stage will also be produced (Tables 11.12.5.1 to 11.12.5.5B).

11.0 Statistical Methods:

In this section we first describe the method to be used for the analysis of the primary outcome. We then describe the principles and methods to be used for descriptive and comparative statistical analyses and tables that will be used to report these.

11.1 Analysis of the primary outcome:

The figure shows how the differences in the proportions with the primary outcome and the two sided 95% CI will be interpreted.

Figure 11.1.1:

95% CI for differences in proportions seropositive (Aerosol - Subcutaneous)

SOP VEL 1/1:	Statistical Analysis Plan	Page 8 of 61
September 11, 2012		

Phase II/III	WHO Measles Aerosol Vaccine	Protocol
Clinical Trial	Project	WHO/MAP/IN/002

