The primary efficacy analysis for safety includes all children vaccinated, according to the route of vaccination that they received and with at least one safety assessment.

In addition, we will summarize explicitly any severe reactions or serious adverse events (SAE) in children vaccinated by the wrong route.

11.5 Timing of Analyses:

The primary efficacy analysis will be conducted after the last enrolled participant completes the day 91 follow up visit.

Every 3 months the data will be analyzed and a report will be made available for the DSMB. This report will focus on safety.

11.6 Method for Handling Missing Data:

For the primary efficacy analysis there is no plan to impute data values for participants who do not complete follow up visits.

For the PP dataset, missing values will be treated as missing at random. However, preliminary analyses such as age, sex, baseline immunogenicity distribution will be studied between the two groups to examine the validity of this assumption.

For the assessment of immunogenicity, missing values (e.g. no blood taken) are treated as if they are missing at random. The OD values for blood samples taken outside the specified time limits will be treated as missing values.

Note that missing values at 91 days post-vaccination and at other time points will be considered for further analyses. The missing information will be handled by best and worst case scenario methods. Where blood specimens are taken outside the recommended time interval, these results will still be used.

11.7 Significance Level:

This is a non-inferiority trial and the confidence interval approach will be used to determine the trial outcome. For additional analyses, such as those adjusting for covariates, we will not use a fixed 'statistical significance' level for reasons described by Sterne and Davey Smith (3). For analyses that require the calculation of p values, we will base our interpretation on examination of the effect size, confidence interval and p value.

11.8 Safety:

We will estimate the proportions (with 95% CI) of AE in each arm according to the definitions of the primary and secondary safety outcomes (Refer section 8.7 in the protocol).

SOP VEL 1/1:	Statistical Analysis Plan	Page 10 of 61
September 11, 2012		

11.9 Covariates to be examined:

Covariates of interest are as follows:

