	persons having AE [#]	sons population ing ** E [#] (in %)	Upper CI	having AE [#]	population ** (in %)	Lower CI	Upper CI	

[#]One subject may have more than one AE. So, 'Number of persons having AE' counts expected to overlap

SOP VEL 1/1:	Statistical Analysis Plan	Page 36 of 61
September 11, 2012		

Phase II/III	WHO Measles Aerosol Vaccine	Protocol
Clinical Trial	Project	WHO/MAP/IN/002

Table 13.1.1E (1): Frequency of adverse events r	reported from 57 days	s to 91 days after
vaccination		

	Aerosol				Subcutaneous			
Adverse Events	Number	% of AE	95% CI for percentage of AE		Number	% of AE	95% CI for perceptage of AE	
	of AEs	/0 01 112	Lower CI	Upper CI	of AEs	/0 01 112	Lower CI	Upper CI

 Table 13.1.1E (2): Number of subjects experiencing at least one adverse event from 57 days to 91 days after vaccination

		Aeros	sol		Subcutaneous			
Adverse Events	Number Proportion of in		95% CI for Population		Number of persons	Proportion in	95% CI for Population	
	persons having AE [#]	population ** (in %)	Lower Upper CI CI	having AE [#]	population ** (in %)	Lower CI	Upper CI	

[#]One subject may have more than one AE. So, 'Number of persons having AE' counts expected to overlap

SOP VEL 1/1:	Statistical Analysis Plan	Page 37 of 61
September 11, 2012		

Phase II/III	WHO Measles Aerosol Vaccine	Protocol
Clinical Trial	Project	WHO/MAP/IN/002

Table 13.1.1F (1): Frequency of adverse events reported from 92 days to 364 days after	er
vaccination	

	Aerosol				Subcutaneous			
Adverse Events	Number	% of AE	95% percenta	CI for ige of AE	Number	% of AE	95% percenta	CI for age of AE
	OI AES		Lower CI	Upper CI	OI AES		Lower CI	Upper CI

 Table 13.1.1F (2): Number of subjects experiencing at least one adverse event from 92 days to 364 days after vaccination

		Aeros	Subcutaneous					
Adverse Events	Number Proportio of in		95% CI for Population		Number of persons	Proportion in	95% CI for Population	
	persons having AE [#]	s population ** (in %)	Lower CI	Upper CI	having AE [#]	population ** (in %)	Lower CI	Upper CI

[#]One subject may have more than one AE. So, 'Number of persons having AE' counts expected to overlap

SOP VEL 1/1:	Statistical Analysis Plan	Page 38 of 61
September 11, 2012		

13.2: Severity of reactions

The Distribution of Severity of Adverse Events:

Table 13.2.1A: Number of AEs reported according to severity in the Aerosol group

		Severity of A		SAE		
Time Points	Mild n (% of events)	Moderate n (% of events)	Severe n (% of events)	Total	events)	

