0-30mins						
31 mins to day 14						
Day15-28						
Day29-56						
Day57-91						
Day 92-364*						
Total						

*Applies to Vadu subset only

Table 13.2.1B: Number of AEs reported according to severity in the Subcutaneous group

Time Points		Severity of A		SAE	
	Mild n (% of events)	Moderate n (% of events)	Severe n (% of events)	Total	n (% of events)
0-30mins					
31 mins to day 14					
Day15-28					
Day29-56					
Day57-91					
Day 92-364*					
Total					

*Applies to Vadu subset only

Phase II/III
Clinical Trial

13.3: Causality

Table 13.3.1A: Number of moderate and severe Adverse Events and relationship to vaccination, Aerosol group

	Relationship to Vaccination						
Time Points	Not Related n (% of events)	Unlikely to be Related n (% of events)	Possible n (% of events)	Probable n (% of events)	Most Probably n (% of events)	Insufficient data to assess n (% of events)	Total
0-30mins							
31 mins to day 14							
Day15-28							
Day29-56							
Day57-91							
Day 92-364*							
Total							

*Applies to Vadu subset only

Table 13.3.1B: Number of moderate and severe Adverse Events and relationship to
vaccination, Subcutaneous Group

	Relationship to Vaccination						
Time Points	Not Related n (% of events)	Unlikely to be Related n (% of events)	Possible n (% of events)	Probable n (% of events)	Most Probably n (% of events)	Insufficient data to assess n (% of events)	Total
0-30mins							
31 mins to day 14							
Day15-28							
Day29-56							
Day57-91							
Day 92-364*							
Total							

*Applies to Vadu subset only

Phase II/III	WHO Measles Aerosol Vaccine	Protocol
Clinical Trial	Project	WHO/MAP/IN/002

13.4: Listing of AEs by subject

Table 13.4.1: AE listing by Subject

subject ID(Sex)	Age (Day)	Vaccinat ed Date	AE	Date of AE onset	Days to start AE	Date of AE stops	Duration of AE existence (in days)	Concomitant Medications given for the Visit	AE treatment outcome

Phase II/III	WHO Measles Aerosol Vaccine	Protocol
Clinical Trial	Project	WHO/MAP/IN/002

14.0 Interim Analyses:

An interim analysis of safety data will be completed for this analysis. This includes only safety assessment events reported within 91 days after vaccination, and no laboratory results will be included. The DSMB will use data from the first 100 children in each arm. This will be done as soon as possible after these data are available.

Table 14.0.1: Frequency of all AEs by study group and time since vaccination

	Time since vaccination																	

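### The final severity tables (SAP 13.2.1A/B) count events as a percentage of events, so the share of vaccinated infants with a moderate or severe AE by route cannot be read from the planned output

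*Supplement*

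**What the plan says.** **Severity.** SAP 13.2 has two shells, Table 13.2.1A for aerosol and 13.2.1B for subcutaneous. The first is titled "Table 13.2.1A: Number of AEs reported according to severity in the Aerosol group". Rows are time windows. Columns are mild, moderate, severe, a total and SAE. The severe column has a heading that begins "Severe n (% of events", and the other grades follow the same pattern. There is no confidence interval and no column for the other arm.

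**Causality.** SAP 13.3 is also event-based: "Number of moderate and severe Adverse Events and relationship to vaccination, Aerosol group", with a matching subcutaneous table.

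**Infants.** Tables 13.1.1A(2) to F(2) count subjects with at least one AE in each window, with a proportion and 95% CI. Their footnote warns: "One subject may have more than one AE". No heading in them mentions grade, and their row stubs are blank.

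**Listings.** "Table 13.4.1: AE listing by Subject" has no severity column and no study-arm column. Table 11.12.5.1 shows arm and severity per infant, but only for infants who discontinued.

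**Denominator and precision.** The safety set in SAP 11.4 "includes all children vaccinated, according to the route of vaccination that they received and with at least one safety assessment". SAP 8.2 states precision per participant: "if no reactions are observed, the upper 95% confidence interval with a sample size of 1000 is 0.37%, or 1 in 270".

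**Room to change.** SAP 9.2 says of the pre-analysis review: "The final format of tables will be decided after this review".

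**The concern.** The trial aims at licensure, which the protocol (sections 5 and 5.2) ties to an acceptable safety profile. For severity, the natural question is how many of the infants vaccinated by each route had a moderate or severe reaction. Moderate is also the protocol's own action threshold: at that grade a field worker must call the On-Call Medical Officer, and causality is reviewed (sections 8.5.1.3 and 8.7).

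A percentage of events does not answer that question, for two reasons. Repeat events in one infant inflate the count. And in Tables 13.2.1A/B the denominator includes mild events, so an arm with more mild reactions shows a smaller severe share for the same number of severe events. Mild reactions may differ by route. Protocol 4.3.2 cites a study of 12-month-olds in which conjunctival inflammation occurred in 57% after aerosol and 35% after subcutaneous vaccine, and none needed medical treatment.

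**Working it through.** **1. The SAP's own precision figure.** Exact (Clopper-Pearson) 95% limits:

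| Observed | Recomputed | SAP Table 8.2.1 |
|---|---|---|
| 0/1,000 | 0.00–0.37% | 0.00–0.37% |
| 10/1,000 | 0.48–1.83% | 0.48–1.83% |
| 0/800 | 0.00–0.46% | 0.00–0.46% |
| 8/800 | 0.43–1.96% | 0.43–1.96% |

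The figures reproduce, and they are per infant.

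**2. Can any final shell give infants by grade?**

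| Shell | Unit | Grade? | Arm? | Coverage |
|---|---|---|---|---|
| 13.2.1A/B | events | yes | one table per arm | all windows |
| 13.3.1A/B | events | moderate and severe pooled | one table per arm | all windows |
| 13.1.1A(2)–F(2) | infants | none specified | yes | one window each |
| 13.4.1 | listing by subject | no | no | AEs by subject |
| 11.12.5.1 | listing by subject | yes | yes | discontinued infants only |

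The tables in SAP 14 and Appendix 1 show AE frequencies or durations. They belong to the interim analysis (first 100 children per arm) and the DSMB reports, and do not give infants by grade in the full safety set. SAP 11.4 also promises an explicit summary of severe reactions, but only for children vaccinated by the wrong route.

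**3. What event counts alone determine.** Let k > 0 be the moderate or severe events in an arm and window. Each affected infant has at least one, so the number of infants lies between 1 and k. With assumed figures, k = 60 in 1,000 infants:

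| Events per affected infant | Infants | Proportion (95% CI) |
|---|---|---|
| 1 | 60 | 6.0% (4.61–7.66) |
| 2 | 30 | 3.0% (2.03–4.26) |
| 4 | 15 | 1.5% (0.84–2.46) |

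**4. What the infant tables add.** Suppose 13.1.1(2) has an any-AE row with M infants, and 13.2.1 shows E mild events in the same window. At most E infants can have mild events only. So the infants with a moderate or severe event number at least max(1, M − E) and at most min(k, M).

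- Assumed M = 300, E = 250, k = 60: 300 − 250 = 50, so the range is 50 to 60.
- Assumed M = 300, E = 400, k = 60: 300 − 400 is negative, so the range is back to 1 to 60.

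The bound can be tight when repeat mild events are few, and it says nothing useful when they are common. It also works window by window. An infant can appear in several windows, so the ranges cannot simply be added to cover days 0–14 or 0–91.

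**5. Effect of the mild denominator (13.2.1 only).** Assume 30 moderate or severe events in each arm, with 300 mild events subcutaneous and 400 aerosol:

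- subcutaneous: 30/(300 + 30) = 9.1%
- aerosol: 30/(400 + 30) = 7.0%

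The percentages differ although the counts are equal. Tables 13.3.1A/B contain only moderate and severe events, so this step does not apply to them.

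**The case against.** The strongest defence is that nothing the plan promises depends on this output. The safety objective is descriptive. The primary safety analysis is the proportion with any AE and the secondary is individual AEs. Both are planned with 95% CIs, and Tables 13.1.1(2) count infants. Termination turns on a single SAE or encephalitis/encephalopathy judged most probably related to aerosol vaccine (SAP 15). Every severe and every serious AE goes to the DSMB (protocol 8.7.3 and 8.7.6). All of this stands. A reader might infer that the event-based tables break SAP 11.8 or the primary safety outcome; they do not, because neither is defined by grade.

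Second, the blank row stubs of 13.1.1(2) could still be filled by grade, since the SAP does put grade in row labels elsewhere (Table 14.0.1). The as-treated flow chart, Figure 11.12.7.3, is not shown. This is fair, so the claim is only that no infant-by-grade table is specified, not that one is excluded.

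Third, the printed counts can be compared between arms under 1:1 allocation. That holds for events, but not for infants at risk unless repeat events are absent or known by grade. The paired 13.1.1(1) and (2) tables give overall events and persons, but not by grade.

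Fourth, SAP 9.2 leaves the format open. That makes the gap easy to close, but it does not specify the table that would close it.

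**Conclusion.** The point holds as a weakness in the chosen unit of analysis. The planned final tables do not determine the proportion of vaccinated infants with a moderate or severe AE by route. At best they bound it, and the bound needs an any-AE row in 13.1.1(2).

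The size and direction of any distortion in this trial are unknown, because the documents give neither severity rates nor repeat-event rates. The figures in steps 3 to 5 of the working are assumed, to show the mechanism only. A reader might infer that the severity summary will flatter one route. The documents do not support that: mild events could be more frequent in either arm, and the event counts are printed beside the percentages. Nor is the whole safety analysis event-based, since the any-AE and individual-AE proportions are per infant.

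The conclusion assumes that the shells are used as drafted. It is a worthwhile, low-cost improvement, not an error that threatens a trial conclusion.

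**What to change.** In Tables 13.2.1A/B, add the number of infants by worst grade (mild, moderate, severe) and with any SAE, over infants vaccinated in the as-treated set of SAP 11.4. Show both arms side by side with 95% CIs.

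Report by window, and cumulatively for two periods:

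- days 0–14, the protocol's acute reactogenicity period (8.7.1);
- days 0–91, the primary safety period (SAP 6.2.1).

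Show Vadu days 92–364 separately on its own denominator. That row covers Vadu only, yet the present shell places it above a common Total row. The event counts can stay beside the infant counts.

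Grades and subject IDs are already collected. Only table shells change, SAP 9.2 permits this, and the cost is slightly longer tables.
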